10.3.2 ADA summaries

The following outputs will be presented on the SS.

Tables:

- Number and percentage of participants with ADA (positive, negative, inconclusive, missing) and NAb (positive, negative, missing) sample status at the time of each visit will be summarized by first dose received and RLZ total. Denominator is the number of study participants having a non-missing result at that visit.
- Number and percentage of participants in each of the individual and combined ADA participant status categories presented in [Table 10-1](#) will be summarized by first dose received and RLZ total at each scheduled visit and EOS visit. The table will be repeated by prior treatment in MG0003 (RLZ total or placebo) up to Week 9.

- Total prevalence of pre-existing ADA and NAb, defined as number and percentage of participants having an ADA positive sample status at baseline, with the denominator being the total number of study participants having an evaluable sample result at baseline. Missing samples will not be included in the denominator. The table will be repeated by prior treatment in MG0003 (RLZ or placebo). The same will be repeated for NAb.
- The first occurrence of treatment-emergent ADA positivity: cumulative number and percentage of TE-ADA positive participants (category 7) who are ADA positive for the first time at each visit. The table will be repeated by prior treatment in MG0003 (RLZ or placebo).
- Summary table of mean maximum percentage CFB in total IgG and mean CFB in MG-ADL, summarized by ADA participant categories 1, 2, 9, 10, 11 and 12 for the corresponding time period of interest and by treatment group and RLZ total [REDACTED].
- Overall summary table of TEAEs at Week 9 and EOS summarized by ADA participant categories 1, 2, 7 and 8 for the corresponding time period of interest.
- Summary of incidence of TEAE at Week 9 and EOS by ADA participant category 1, 2, 7 and 8 for the corresponding time period of interest.
- Summary table of AEOF hypersensitivity reactions, anaphylactic reactions and infusion reactions at Week 9 and EOS by ADA participant category 1, 2, 7 and 8 for the corresponding time period of interest.

Figures:

- Individual time course plots for ADA positive study participants with at least one ADA positive sample, representing ADA and NAb titers (on log-scale), percentage CFB for total IgG and MG-specific autoantibodies, and CFB for MG-ADL total score. The sub-title of the graph will include the study participant number, bodyweight category, treatment group (including prior treatment group in MG0003), and individual ADA participant category (3, 4, 5, 6) up to EOS. The dosing will be represented in the x-axis with bars/arrows at the time of dose.
- Spaghetti plots of individual time course of ADA titer for ADA positive participants in categories 9, 10, 11 and 12 (determined through EOS), whereby all categories are overlaid on the same plot and visualized using different symbols and colors. The ADA titer results will be presented on a log-scale. Dosing time points should be indicated below the x-axis. The same plot will be repeated for NAb titer for NAb positive participants in categories 9 and 11.
- A box-and-whisker plot of maximum postdose ADA titer (on log-scale) through Week 5, Week 9, Week 52 and EOS versus ADA participant category for categories 9, 10, 11 and 12 (determined for the corresponding time period of interest). The same plot will be repeated for NAb titer for ADA participant categories 9 and 11.
- Time course plot of mean CFB in MG-ADL total score, summarized by ADA participant category 1, 2, 9, 10, 11 and 12. Categories will be determined for the time period from baseline up to timepoint of interest (Week 5, 9, 52 and EOS). Separate plots for each treatment group and RLZ total [REDACTED].

- Spaghetti plots of individual time course of percentage CFB for total IgG, for each of the ADA participant categories 1, 2, 9, 10, 11 and 12 and time period of interest (Baseline up to Week 5, Week 9, and EOS) whereby the ADA participant categories are multipaneled. Separate plots for each treatment group and RLZ total [REDACTED]. Individual samples that tested positive for ADA will be visualized using a symbol and/or color. Dosing time points should be indicated below the x-axis.
- Scatter dot plot of individual CFB in MG-ADL total score categorized by ADA titer tertile (including category ADA not present) for each scheduled assessment (Week 5, 9, 21, 33, 45, 52, and 60). The same plot will be repeated for NAb titer.
- Scatter dot plot of individual percentage CFB for total IgG categorized by ADA titer tertile (including category ADA not present) for each scheduled assessment (Week 5, 9, 21, 33, 45, 52, and 60). The same plot will be repeated for NAb titer.

Listing:

- By-subject listing by treatment group and timepoint, of ADA and Nab sample status, ADA titer, NAb titer, rozanolixizumab plasma concentration, percentage CFB for total IgG and IgG subclasses, CFB for MG-specific autoantibodies, CFB for MG-ADL total score, QMG and MG-C. In addition, the time since administration of IMP will be reported (in days).

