already started MG0004, a minimum treatment duration of 6 visits must be completed (if IMP treatment is withheld for low IgG, study participants missed dose(s) can be counted as part of the total 6 visits for completion of MG0004 and meet eligibility requirements for MG0007) and then the participant will discontinue MG0004 and have the opportunity to enter into MG0007. For study participants entering MG0007 from the treatment period of MG0004, he/she must complete the PEOT Visit in MG0004 which will serve both as the Screening Visit for MG0007 and as the EOS for MG0004. If a study participant completes the Treatment Period and is in the Observation Period of MG0004, he/she will then complete the EOS visit to serve as the Screening Visit for MG0007. Once the site is active for MG0007, no further participants will enroll in MG0004 and the study will be closed at the site once all eligible study participants have rolled over into MG0007.

An IDMC will be formed to monitor the ongoing safety of the study. The IDMC will review implications of individual and cumulative cases to continuance of the study in an ongoing fashion.

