3 DATA ANALYSIS CONSIDERATIONS

3.1 General presentation of summaries and analyses

Statistical analysis and generation of tables, figures, participant data listings, and statistical output will be performed using SAS[®] Version 9.3 or higher. All tables and listings will use Courier New font size 9.

Descriptive statistics will be displayed to provide an overview of the study results. For continuous variables, descriptive statistics will include number of participants with available measurements (n), mean, standard deviation (SD), median, minimum, and maximum.

For categorical variables, the number and percentage of participants in each category will be presented. Unless otherwise noted, the denominator for percentages will be based on the number of participants included in the respective analysis set. Participants with missing data can generally be accounted for using the following approaches:

- For summaries of demographics and Baseline characteristics: summarize percentages based on all participants in the analysis set and include a “Missing” category (corresponding to participants with missing data for the variable being summarized) as the last row in the list of categories being summarized.
- For summaries of efficacy and safety endpoints, unless otherwise specified: summarize percentages based only on those participants with observed data for the variable being summarized. As the denominator may be different from the number of participants in the analysis set being considered, the denominator should be displayed in the table. The general format for displaying this will be “n/Nsub (%)”.

Unless otherwise noted, all percentages will be displayed to one decimal place. No percentage will be displayed for zero counts, and no decimal will be presented when the percentage is 100%.

For PK concentration data, summary statistics will include geometric mean, geometric coefficient of variation (geoCV), 95% confidence intervals (CIs) for geometric mean, arithmetic mean, SD, median, minimum, and maximum.

Decimal places for descriptive statistics will always apply the following rules:

- “n” will be an integer;
- Mean (arithmetic, geometric), SD, and median will use one additional decimal place compared to the original data;
- geometric CV [%] will be presented with one decimal place;
- Minimum and maximum will have the same number of decimal places as the original value.

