10.3.1 Data consideration

ADA Sample Status

The ADA sample status will be determined for each pre-treatment (Baseline) and post-treatment (post-Baseline) visit where samples are taken for ADA analysis.

- Sample values that are either 'negative screen' or 'positive screen' and 'negative immunodepletion' will be defined as **ADA negative** if corresponding rozanolixizumab concentrations are equal or below the validated drug tolerance limit of the ADA assay (200µg/mL rozanolixizumab) allowing detection of 100ng/mL ADA
- Sample values that are either 'negative screen' or the combination of 'positive screen' and 'negative immuno-depletion', but with corresponding rozanolixizumab concentrations above the validated drug tolerance limit of the ADA assay, will be defined as **ADA inconclusive**
- Sample values that are 'positive screen' and 'positive immunodepletion' will be defined as **ADA positive**
- Samples that could not be tested for ADA status due to inadequate sample volume, mishandling, or errors in sample collection, processing, storage, etc., will be defined as **Missing**.

Note: if a participant has no baseline ADA, then she/he can't be treated as "Inconclusive".

Neutralizing antibody (NAb) sample status (positive/negative/missing) will be determined for ADA positive samples. Samples that are NAb positive will be evaluated in a titration assay to quantify the NAb level and will be reported as titer.

Definition of ADA Baseline

Baseline for ADA should be the last measurement prior to receiving the very first rozanolixizumab (RLZ) infusion in either MG0004 or the feeder study MG0003. Specifically, baseline for ADA is defined as:

- MG0003 ADA baseline if participants randomized to RLZ groups in MG0003 (note: MG0003 post-baseline ADA samples will not be considered for the ADA participant status in MG0004);
- MG0004 ADA baseline if participants randomized to placebo in MG0003.

If the ADA sample status for the visit prior to the first dose of RLZ is missing, the last non-missing sample will be used.

ADA/NAb Participant Status

The ADA participant status will be classified on study participant and group level as outlined below (Shankar et al. 2014; Rup et al, 2015). A description of how study participants will be categorized for the immunogenicity assessment is provided in

Table 10-1.

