Individual study participants will be assessed for ADA participant status, composed of 6 categories: ADA negative, inconclusive, and ADA positive, whereby a positive participant’s status is determined as originating from a treatment-induced, boosted, reduced or unaffected ADA response.

Study participants who are identified as being treatment-induced or treatment-boosted ADA-positive will be grouped as treatment-emergent (TE)-ADA positive participants. Study participants who are identified as being treatment-reduced or treatment-unaffected ADA-positive will be grouped as non-TE-ADA positive participants. Both TE-ADA positive and non-TE-ADA positive participants will be further classified as NAb negative or NAb positive.

The individual and combined ADA participant categories will be derived and summarized through each of the scheduled sampling points (ie Week 5, 9, 21, 33, 45, 52 and 60) and EOS visit, unless specified otherwise.

Table 10-1: Terms and Definitions for ADA Status Evaluation in Study Participant

Classification	Classification Label	Definition
Individual participant categories		
1	Pre-ADA negative – treatment induced ADA negative (ADA-NEG)	Study participants who have an ADA negative sample at Baseline and at all sampling points post-Baseline up to the timepoint of interest.
2	Inconclusive	Study participants who have an ADA positive or negative Baseline sample and some post-Baseline samples are missing or inconclusive, while other post-Baseline samples are ADA negative up to the timepoint of interest.
3	Pre-ADA negative – treatment induced ADA positive (TI-POS)	Study participants who have an ADA negative sample at Baseline and have at least one ADA positive sample at any sampling point post-Baseline up to the timepoint of interest.
4	Pre-ADA positive – treatment boosted ADA positive (TB-POS)	Study participants who have an ADA positive sample at Baseline and at least one ADA positive sample at any sampling point post-Baseline up to the timepoint of interest, with increased titer values compared to Baseline (greater than a predefined fold difference increase from Baseline value which will be defined within the validation of the assay i.e. MSR of the assay).

5	Pre-ADA positive – treatment reduced ADA positive (TR-POS)	Study participants with an ADA positive sample at Baseline, and ADA negative samples at all sampling points post-Baseline up to the timepoint of interest.

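### The Missing row in the ADA/NAb sample-status table is a percentage of participants who are not missing; Table 10-1 also merges lost samples with assay interference and leaves MG0007 leavers unclassified at later weeks

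*SAP*

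**What the plan says.** SAP 10.3.2 begins its list of tables with the number and percentage of "participants with ADA (positive, negative, inconclusive, missing) and NAb (positive, negative, missing) sample status at the time of each visit", by first dose received and in total. The base for those percentages follows: "Denominator is the number of study participants having a non-missing result at that visit".

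Elsewhere the SAP keeps two conventions apart. Section 3.1 pairs a Missing category with an all-participants denominator for demographics and baseline data. For efficacy and safety endpoints it says to "summarize percentages based only on those participants with observed data for the variable being summarized". The table of pre-existing ADA prevalence, later in the 10.3.2 list, leaves missing samples out of the denominator and has no missing row.

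At sample level, SAP 10.3.1 defines Missing as "Samples that could not be tested for ADA status due to inadequate sample volume, mishandling, or errors in sample collection", and adds processing and storage faults. It reserves inconclusive for samples that are not confirmed positive and were taken with drug concentration above the assay's tolerance limit (200 µg/mL).

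At participant level, Table 10-1 category 1 (ADA negative) needs a negative sample at Baseline and "at all sampling points post-Baseline up to the timepoint of interest". Category 2 (Inconclusive) takes participants for whom "some post-Baseline samples are missing or inconclusive, while other post-Baseline samples are ADA negative up to the timepoint of interest". Status is tabulated at Weeks 5, 9, 21, 33, 45, 52 and 60 and at EOS.

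Protocol 4.1 lets participants leave for MG0007, but "a minimum treatment duration of 6 visits must be completed" first. For those leaving from the Treatment Period, the PEOT visit also serves as EOS. SAP 3.2.3 maps PEOT assessments to the next scheduled site visit at which that assessment is due.

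**The concern.** A percentage needs its numerator to be part of its denominator. In the Missing row it is not, so the figure is a ratio of missing to non-missing results presented as a proportion. A reader would take it as the share of samples lost, and it always overstates that share. The columns also fail to add to 100%, which invites doubt about the rows that are correct.

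The secondary point concerns interpretation. Category 2 is set beside category 1 in the IgG, MG-ADL and TEAE outputs by ADA status. An Inconclusive label could mean that drug masked the assay or simply that a tube was lost. These have different implications for immunogenicity, and the table cannot separate them. The plan also gives no rule for people who left MG0004 before a fixed week at which status is reported.

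**Working it through.** The plan states no missing rate, ADA rate or target figure, so there is nothing of its own to reproduce. The rates below are assumptions used to show size.

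**Missing row.** Let m be the true share missing among participants due for a sample at a visit.

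- Printed Missing percentage under SAP 10.3.2 = m / (1 − m)
- Sum of the four ADA rows = 1 + m / (1 − m)
- Positive, negative and inconclusive rows together = 100%, because all three sit inside the non-missing base

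| True missing share | Calculation | Printed Missing row | Sum of rows |
|---|---|---|---|
| 5% | 5/95 | 5.3% | 105.3% |
| 10% | 10/90 | 11.1% | 111.1% |
| 20% | 20/80 | 25.0% | 125.0% |
| 50% | 50/50 | 100% | 200% |

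The row exceeds 100% only if more than half the samples are missing. With everyone due as the denominator, a 10% share prints as 10.0%.

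**One missing sample and category 2.** Table 10-1 sets no minimum number or share, so one missing sample is enough. Take a participant who would be negative throughout, with k post-Baseline samples, each lost independently with probability p (assumed). Category 2 also needs at least one negative sample, so

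P(Inconclusive) = 1 − (1 − p)^k − p^k

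| p | Through Week 9 (k = 2) | Through Week 60 (k = 7) |
|---|---|---|
| 1% | 2.0% | 6.8% |
| 2% | 3.9% | 13.2% |
| 5% | 9.5% | 30.2% |
| 10% | 18.0% | 52.2% |

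None of these participants has a sample affected by drug interference. The same rule moves a Baseline-positive participant with later negative samples from category 5 to category 2.

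**Participants who leave for MG0007.** Someone leaving after Visit 6 has a Week 5 sample and a PEOT sample, which SAP 3.2.3 maps to Week 9. Both points through Week 9 are filled. At Weeks 21, 33, 45 and 52 there is no sample.

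- Category 1 asks for negatives at all sampling points up to the week, which this person does not have.
- Category 2 asks for missing or inconclusive samples, but a sample never due is not one that could not be tested.

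Read literally, neither category clearly applies. That is a gap in the rule.

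**The case against.** The best case against this point is that it is small. The study is descriptive, with no testing (SAP 4.1). The substantive percentages are right, counts appear beside every percentage, and the SAP 3.1 default of showing n/Nsub would expose the base. All of that stands, but none of it repairs the Missing row: an entry such as 10/90 (11.1%) displays the contradiction.

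The Inconclusive rule can also be defended. It is explicit and conservative, and the SAP cites published terminology for it. That stands too. Not calling an incomplete negative record negative is a reasonable choice. What remains is that two causes share one label.

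A reader might go further in four ways that the documents do not support.

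- *Transfers to MG0007 necessarily become Inconclusive.* The SAP does not say so. Its definition of Missing covers samples that could not be tested, and Protocol 4.1 makes PEOT the EOS for transfers from the Treatment Period, so nothing need be missing through a participant's own EOS. SAP 2.3 is looser, with PEOT serving as MG0007 Screening or as EOS, so the point is unsettled.
- *The TEAE comparisons by ADA category are distorted by transfers.* Those tables, and the hypersensitivity, anaphylaxis and infusion-reaction table, are at Week 9 and EOS only. Among outputs that name their timepoints, the exposed ones are the status table at later weeks and the Week 52 MG-ADL plot.
- *The ADA objective is misreported at all late timepoints.* The objective is incidence and emergence. One positive sample after a negative Baseline sets category 3, and one boosted sample sets category 4, whatever else is missing. Counts in categories 3, 4 and 7 do not change under the rule.
- *The Missing row will run to 100% or more late in the study.* That requires counting departed participants as missing, contrary to the SAP's definition, and more than half absent.

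**Conclusion.** The main point holds from the text alone: the Missing percentage for ADA and NAb is wrong as written, and nothing elsewhere in the SAP corrects it. The error is modest at low missingness (5.3% printed for 5%) and grows with it (25.0% for 20%). It is confined to that row and to the column totals.

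The secondary point holds as a lack of clarity. A single missing sample is enough for Inconclusive, lost samples and drug interference are merged, and leavers have no stated classification at Weeks 21 to 52. The size of the one-sample effect depends on the assumed loss rate and on independence between samples. The SAP (4.2.3) does expect COVID-19 to cause missing data, but it gives no rate for ADA samples.

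**What to change.** In SAP 10.3.2, show Missing as a count without a percentage, or give it its own denominator: participants due for a sample at that visit while still in MG0004 and, for NAb, those with an ADA-positive sample at that visit. Keep the non-missing denominator for the other rows.

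In SAP 10.3.1 and Table 10-1:

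- State that samples never due because the participant had left MG0004 are not counted as missing, and say whether leavers stay in the table at later weeks.
- Print the number still in study at each timepoint. The by-visit participant count in SAP 5.1 already supplies most of this.
- Report Inconclusive in two lines: missing sample, and concentration above the drug-tolerance limit.

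The cost is SAP wording, a table-shell edit and one derivation flag, with no new samples. There is one trade-off. If leavers are kept, a negative status shown at Week 52 may rest on two early samples and could understate late immunogenicity. If they are dropped, the later columns describe only those who stayed. Either choice is defensible if it is stated and the number still in study is shown.

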6	Pre-ADA positive – treatment unaffected ADA positive (TU-POS)	Study participants with an ADA positive sample at Baseline and an ADA positive sample at any sampling point post-Baseline up to the timepoint of interest, with titer values of the same magnitude as Baseline (less than a predefined fold difference from the Baseline value which will be defined within the validation of the assay, i.e. MSR of the assay ¹).
Combined participant categories		
7	Treatment emergent ADA positive (TE-POS)	Includes study participants who are treatment induced ADA positive (category 3) or treatment boosted ADA positive (category 4).
8	Non-treatment emergent ADA positive (Non-TE-POS)	Includes study participants who are treatment reduced ADA positive (category 5) or treatment unaffected ADA positive (category 6).
9	Treatment emergent ADA positive – NAb positive (TE-POS, NAb-POS)	Includes study participants who are treatment emergent positive (category 7) and have at least one NAb positive sample.
10	Treatment emergent ADA positive – NAb negative (TE-POS, NAb-NEG)	Includes study participants who are treatment emergent positive (category 7) and have no NAb positive samples.
11	Non-treatment emergent ADA positive - NAb positive (Non-TE-POS, NAb-POS)	Includes study participants who are non-treatment emergent positive (category 8) and have at least one NAb positive sample.
12	Non-treatment emergent ADA positive - NAb negative (Non-TE-POS, NAb-NEG)	Includes study participants who are non-treatment emergent positive (category 8) and have no NAb positive samples.
¹ The fold difference increase from baseline value, i.e. the minimum significant ratio (MSR=1.36) determined during assay validation, will be reported in the relevant tables, listings and figures. It reflects the fold difference in titer level that considered higher than the assay variation in titer determination.		

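### SAP 10.3.2 counts treatment-emergent ADA at the first ADA-positive sample, a rule that treatment-boosted participants, already positive at Baseline, cannot meet at any later visit

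*SAP*

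**What the plan says.** The table is headed "The first occurrence of treatment-emergent ADA positivity" (SAP 10.3.2). The rule that fills it is the "cumulative number and percentage of TE-ADA positive participants (category 7) who are ADA positive for the first time at each visit", and it is repeated by prior MG0003 treatment (RLZ or placebo) with no limit on visits.

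The terms come from SAP 10.3.1 and Table 10-1:

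- A sample's ADA status depends on screening and confirmation only: "Sample values that are 'positive screen' and 'positive immunodepletion' will be defined as" ADA positive. Titer plays no part.
- "Baseline for ADA should be the last measurement prior to receiving the very first rozanolixizumab (RLZ) infusion", in either MG0003 or MG0004. It is a pre-treatment sample for everyone.
- Category 7 is the union of category 3 (treatment-induced) and category 4 (treatment-boosted).
- Category 4 is defined as "Study participants who have an ADA positive sample at Baseline and at least one ADA positive sample at any sampling point post-Baseline", "with increased titer values compared to Baseline". The rise must exceed the "minimum significant ratio (MSR=1.36) determined during assay validation".

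**The concern.** The heading names one event and the rule counts another. For a treatment-induced participant the two coincide, because the first positive sample is the treatment-emergent event. For a treatment-boosted participant they do not: the first positive sample is the Baseline sample, and what makes the response treatment-emergent is a later rise in titer, which the rule does not mention.

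The stake is a table that leaves out part of the population it is meant to describe and does not reconcile with the category 7 total in the table next to it. It matters most in the split by prior MG0003 treatment, where the adjacent table stops at Week 9.

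**Working it through.** The plan states no count or rate for this table, so there is no figure to reproduce. The check applies the SAP's own definitions.

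**Logic**

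1. Category 7 includes category 4 (Table 10-1).
2. Every category 4 participant has an ADA-positive sample at Baseline (Table 10-1).
3. Baseline precedes the first rozanolixizumab infusion (SAP 10.3.1).
4. The table places a participant at the visit of the first ADA-positive sample (SAP 10.3.2), and ADA positive carries no titer condition (SAP 10.3.1).
5. So for every category 4 participant the first positive sample is the Baseline one, and none can be first positive at a post-Baseline visit.

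**Illustration with assumed titers**

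The visits are the Weeks 5, 9, 21, 33, 45, 52 and 60 listed in SAP 10.3.1. There are five category 7 participants. A, B and C are negative at Baseline and first positive at Weeks 9, 5 and 33. D and E have a Baseline titer of 50, so the boost threshold is 1.36 × 50 = 68. D stays at 50 at Weeks 5 and 9, then is at 100 from Week 21. E is negative at Week 5, at 50 from Week 9 to Week 33, then at 200 from Week 45.

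| Participant | First positive sample (literal rule) | First post-Baseline positive sample | First visit meeting the category 3 or 4 criterion |
|---|---|---|---|
| A (induced) | Week 9 | Week 9 | Week 9 |
| B (induced) | Week 5 | Week 5 | Week 5 |
| C (induced) | Week 33 | Week 33 | Week 33 |
| D (boosted) | Baseline | Week 5 | Week 21 |
| E (boosted) | Baseline | Week 9 | Week 45 |

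Cumulative counts by visit:

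| Dating rule | W5 | W9 | W21 | W33 | W45 | W52 | W60 |
|---|---|---|---|---|---|---|---|
| Literal, post-Baseline rows | 1 | 2 | 2 | 3 | 3 | 3 | 3 |
| First post-Baseline positive, final category applied backwards | 2 | 4 | 4 | 5 | 5 | 5 | 5 |
| First visit meeting the treatment-emergent criterion | 1 | 2 | 3 | 4 | 5 | 5 | 5 |
| Category 7 row of the per-visit category table | 1 | 2 | 3 | 4 | 5 | 5 | 5 |

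Only the third rule reproduces the category 7 row. The literal rule ends at 3 instead of 5; the shortfall of 5 − 3 = 2 is the number of boosted participants.

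**General size**

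Let N7 be the category 7 total and s the share of it that is category 4. The literal table ends at N7 × (1 − s). The documents do not give s. With N7 = 20 assumed:

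- s = 0: 20 × 1 = 20, no shortfall
- s = 5%: 20 × 0.95 = 19
- s = 30%: 20 × 0.70 = 14

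**The case against.** The strongest reply is that the heading makes the intent plain, and a programmer who reads rule and heading together would date boosted participants at the boost. Table 10-1 supports this: each category is evaluated cumulatively to whichever visit is being summarised. Participant D is treatment-unaffected (category 6) through Week 5 and enters category 7 only at Week 21. In addition, the per-visit table of Table 10-1 categories already gives the cumulative category 7 count with boosted participants correctly placed, and the individual time-course plots and the by-subject titer listing show each boost. Table shells, which SAP 14.1 mentions but which are not among the documents, might settle the point in a footnote.

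Much of this stands, and it rules out three stronger readings that a reader might infer.

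- **Boosted participants will be shown with a pre-treatment onset.** Baseline is not among the sampling points listed for the participant categories, and pre-existing ADA has its own table. The literal outcome is omission, not a Baseline row.
- **Boosted responses will be dated too early.** This needs the EOS category to be applied retrospectively and combined with the first post-Baseline positive sample. SAP 10.3.2 says explicitly when it fixes categories through EOS, as it does for some figures, and does not say so for this table.
- **Boosted responses go unreported in the study.** The per-visit category table reports them.

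What the reply does not cure is the rule itself. Its wording still excludes category 4 and conflicts with its heading. The adjacent table is repeated by prior MG0003 treatment only up to Week 9, so at Weeks 21, 33, 45, 52 and 60 it cannot stand in for that split. Unseen shells cannot be relied on to correct it.

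**Conclusion.** The point holds as a defect in a stated counting rule. Applied as written, it leaves every treatment-boosted participant out of the post-Baseline rows, and the final cumulative count is below the category 7 total by the number of category 4 participants.

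The consequence is minor. The table is descriptive, no testing is planned, and no primary safety or efficacy conclusion rests on it. The shortfall depends on how many category 4 participants occur; the counts and shares shown in the working are assumptions, and with none in category 4 nothing changes. Overall, the per-visit category table offsets the defect. The exception is the split by prior MG0003 treatment after Week 9, where this is the only table in SAP 10.3.2 specified to show cumulative treatment-emergent ADA. An error in the final output is not certain, since a programmer may follow the heading instead of the rule.

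**What to change.** Reword the rule in SAP 10.3.2 to count category 7 participants who first meet the treatment-emergent criterion at each post-Baseline visit, defined as:

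- category 3: the first post-Baseline ADA-positive sample;
- category 4: the first post-Baseline sample with a titer above Baseline by more than the MSR (1.36).

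State that the final cumulative count must equal the category 7 total, and apply the same rule to the repeat by prior MG0003 treatment. The cost is one SAP sentence, one derived onset date and one reconciliation check. No new data are needed.
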